5.1 Primary objective

- To evaluate the pharmacokinetics and pharmacodynamics of emapalumab in healthy Japanese subjects following a single intravenous dose of emapalumab

5.1.1 Primary endpoint

- PK parameters: Cmax, tmax, CEOI, AUClast, AUCinf, %AUCextr, λ_z , $t_{1/2}$, CL, Vss, MRTlast and MRTinf.
- PD biomarkers:
 - Pre-dose circulating IFN γ concentration
 - Total IFN γ concentrations
 - CXCL9 concentration
 - sIL2R concentration

5.2 Secondary objectives

- To assess safety in healthy Japanese subjects following a single intravenous dose of emapalumab
- To investigate immunogenicity of emapalumab.

5.2.1 Secondary endpoints supporting the secondary objective(s)

- Adverse Events
- Laboratory parameters
- The presence of anti-drug antibodies (ADAs) and neutralizing antibodies (nAbs)

6 Investigational plan

[figure not shown]
6.1 Overall study design and plan

This is a randomized, placebo-controlled and double-blinded study to evaluate the PK, PD and safety of a single dose (1 mg/kg) of emapalumab in adult healthy Japanese subjects, performed in Japan. The subjects, 8 in total, will be randomized to receive either emapalumab or matching placebo in a 3:1 ratio (emapalumab: placebo).

Figure 1 shows the study design.

Study subjects will be screened within 21 days prior to administration of investigational medicinal products (IMP). An additional visit will take place within 96 hours prior to IMP infusion for collection a PCR test for SARS-CoV-19. Eligible subjects will be admitted to the clinical unit the day before drug administration (Study Day -1). On Day 1 of the admission period subjects will receive a single dose of emapalumab (1 mg/kg) or placebo administered as a 1-hour infusion. Subjects will be discharged from the unit on Day 8. PK samples will be collected for up to week 14 in order to measure the emapalumab serum levels during at least 3 times the terminal half-life (a total of approximately 3 months). All subjects will be followed-up on regular visits for a minimum of 14 weeks after single infusion of emapalumab. In addition, any subject with ongoing SAEs at study completion will be followed-up until resolution.

Figure 1 **Study Design**

6.2 Dosing Strategy

Since more than 100 patients have been treated and there are no significant safety concerns, a sentinel dosing strategy is not planned for the study. The investigator will evaluate safety and tolerability data (AEs, laboratory data, vital signs, and ECG) continuously in the study and determine if it remains acceptable to continue dosing.

In case emergency unblinding of IMP is required, the investigator will have access to randomization codes (in sealed envelopes).

6.3 Stopping Rules

The trial may be prematurely terminated if warranted on safety grounds. The severity of the observed events shall be graded as mild, moderate or severe.

Dosing will be stopped in the event of:

- One or more subjects demonstrate an immediate infusion reaction that fulfils the following criteria:
 - Severe and
 - does not respond to symptomatic treatment, and
 - has a duration of more than 2 hours

- Two or more subjects report a severe treatment emergent AE or a severe laboratory safety test result
- One or more subjects develop a treatment emergent serious (life-threatening or fatal) AE at any time during the study
- The investigator considers the AE profile or the laboratory safety assessment to indicate an unacceptable risk to the well-being of trial subjects

The study may be terminated by the sponsor at any time for any reason. This may include reasons related to benefit-risk, practical, regulatory or medical reasons.

6.3.1 Stopping Rules for individual subject

As per the judgement of the investigator:

- In the event of any severe events, administration of IMP to the individual subject must be discontinued.
 - If an event, considered to be mild or moderate, occurs during the infusion, the subject shall be treated as the investigator deems appropriate and may continue receiving the single infusion.
 - In the event of appearance of mild or moderate local infusion site reactions during the infusion, the infusion rate may be lowered. However, infusion time should not exceed two hours.

Subjects for whom IMP administration has stopped will be followed-up as per protocol.

6.3.2 Emergency Treatment

This study will be conducted at a single center (Phase I Unit) under the supervision of the principal investigator. The Phase I Unit is equipped with emergency care facilities to provide a safe environment for the study. Subjects in this study will be hospitalized from the day before treatment until 8 days after and immediate access to medical staff and equipment necessary for emergency treatments are available.

In case of hypersensitivity reaction, immediate treatment is given at the discretion of the investigator. Depending on symptoms, this may e.g., be antipyretics such as acetaminophen (paracetamol), corticosteroids or additional antihistamines, epinephrine and bronchodilators in case of severe hypersensitivity reactions (e.g. anaphylaxis) Necessary equipment for resuscitation must be available during study drug infusion.

6.4 Discussion of study design, including the choice of control groups

The study is designed to investigate safety, PK/PD in Japanese healthy subjects. The investigator, study subjects and sponsor will be blinded to treatment allocation (placebo vs. active) to avoid reporting, assessment and allocation biases.

6 subjects are considered sufficient, considering the inter-subject variability in the PK results in the NI-0501-03 study and 2 placebo is considered a reasonable number of subjects.

6.5 Selection of study population

6.5.1 Inclusion criteria

A subject must fulfill the following criteria in order to be included in the study:

1. Healthy Japanese (male and female) subjects between 20 and 50 years (inclusive).
2. Body weight greater than 45 kg (female) or 50 kg (male) and a body mass index (BMI) $>18 \text{ kg/m}^2$ and $<30 \text{ kg/m}^2$ (BMI= weight (kg) / height (m) 2)
3. Vital signs in the following range:
 - Axillary body temperature: 35.2 – 37,5
 - Heart rate (after at least 3 minutes of rest, measured in the supine position): 40-100 bpm
 - BP $< 140/80$, mean of 3 readings after 15 minutes rest
4. Haemoglobin level equal or above 11 g/dL in females and 13 g/dL in males.
5. Subject having C-reactive protein (CRP) levels within the normal range (local laboratory range).
6. Women of child-bearing potential, defined as all women physiologically capable of becoming pregnant **having agreed to use highly effective methods of contraception** during dosing and for 6 months after receiving IMP.

Highly effective contraception methods include:

- Total abstinence (when this is in line with the preferred and usual lifestyle of the patient). Periodic abstinence (e.g., calendar, ovulation, symptothermal, post-ovulation methods) and withdrawal are not acceptable methods of contraception.
- Female sterilization (have had surgical bilateral oophorectomy with or without hysterectomy), total hysterectomy, or tubal ligation at least six weeks before taking study treatment. In case of oophorectomy alone, only when the reproductive status of the woman has been confirmed by follow up hormone level assessment.
- Male sterilization (at least 6 months prior to screening). For female patients on the study, the vasectomized male partner should be the sole partner for that patient, otherwise highly effective methods to be applied.
- Use of oral, (estrogen and progesterone), injected or implanted hormonal methods of contraception or placement of an intrauterine device (IUD) or intrauterine system (IUS),

or other forms of hormonal contraception that have comparable efficacy (failure rate <1%).

- In case of use of oral contraception women should have been stable on the same brand (or generic equivalent) for a minimum of 3 months before taking study treatment. Women are considered post-menopausal and not of child bearing potential if they have had 12 months of natural (spontaneous) amenorrhea with an appropriate clinical profile (e.g., age appropriate, history of vasomotor symptoms) or have had surgical bilateral oophorectomy (with or without hysterectomy) or tubal ligation at least six weeks ago.
- 7. Signed informed consent.

6.5.2 Exclusion criteria

The presence of any of the following will exclude a subject from inclusion in the study:

1. Any clinically significant abnormality in the results of the safety laboratory tests. Subjects presenting a minor deviation from laboratory ranges could be enrolled if the investigator judge it to be non-clinically significant
2. Any clinically significant abnormality on the screening electrocardiogram (ECG), as judged by the investigator
3. History or clinical evidence of any disease and/or existence of any surgical or medical condition that might interfere with the absorption, distribution, metabolism or excretion of the study drugs
4. Actual presence or occurrence of any bacterial, viral, parasitic or fungal infection within the 4 weeks preceding IMP infusion
5. Positive results from serology examination for Hepatitis B surface antigen (HBsAg), Hepatitis C Virus (HCV), Human Immunodeficiency Virus (HIV), syphilis (TP-antigen and RPR) or pregnancy
6. Positive stool test for Shigella or salmonella infection.
7. Positive results from Sars-CoV-19 screening within 96 hours prior to randomization
8. History or clinical evidence suggestive of active or latent tuberculosis at screening. (i.e. test positive to the IFN γ -release assay)
9. History or presence of any severe allergic reactions
10. Suspected hypersensitivity to any component of the drug formulation.
11. History or presence of any malignancy
12. History or presence of drug or alcohol abuse
13. Subject with a smoking history within the last 6 months prior to the time of screening
14. Immunization with a live vaccine within 6 weeks prior to receiving IMP and 12 weeks after IMP infusion

15. Experience of collected blood corresponding to any of the following
 - Component blood donation within 2 weeks before the screening test and within 2 weeks before the first study drug administration
 - Collection of 200 mL or more of blood (blood donation, etc.) from 4 weeks before the screening test until admission
 - Collection of 400 mL or more of blood (blood donation, etc.) from 12 weeks before the screening test until admission
16. Usage of any prescription drugs within 2 weeks or over-the-counter medication including herbal supplements (with the exception of multi-vitamins) within 1 week before IMP administration without prior approval from the investigator
17. Positive pregnancy test at screening or Day -1
18. Any circumstances or conditions, which, in the opinion of the investigator, may affect the subject's full participation in the study or compliance with the protocol
19. Enrollment in another concurrent clinical interventional study, or intake of another IMP, within four months or 5 half-lives (of the other IMP) prior to inclusion in this study

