4.1.2.2.2 Toxicology

Binding and functional data demonstrated Rhesus and Cynomolgus monkeys to be relevant species to evaluate the safety of emapalumab. No off-target toxicity was attributed to the drug when administered to Cynomolgus monkeys in 13 weekly doses of up to 200 mg/kg. Shigella and Campylobacter infections were observed at all dose levels (10 to 200 mg/kg/week) in animals originally harboring gastrointestinal pathogens (Shigella, Salmonella, Campylobacter) prior to emapalumab administration. These findings were assessed to be in line with emapalumab pharmacological effect (i.e., neutralization of IFN γ), given the role played by IFN γ in controlling these pathogens. Subsequently, in a study where cynomolgus monkeys were free from gastrointestinal pathogens at Screening, weekly administrations of emapalumab for 8 consecutive weeks at doses up to 30 mg/kg were well tolerated with no toxicity or gastrointestinal disturbances observed, and no need for antibiotic prophylaxis.

Results from a human tissue cross-reactivity study, involving a panel of 35 different human tissues, demonstrated that emapalumab did not cross-react with any of the human samples tested.

Embryo-fetal development, fertility and early embryonic development as well as peri- and post-natal development studies were performed in mice. No effects on embryo-fetal development, mating or fertility were observed. No effects on sexual maturation, organ weights, learning and memory, reproductive or immunological functions evaluated in the F1 generation mice were observed.

More details are available in the current version, 10.0 dated 24Jan2020, of the Investigator Brochure.

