6.6.3 Methods of assigning subjects to treatment groups

A single intravenous dose of 1 mg/kg is considered relevant for this Phase 1 study in Japanese healthy subject to bridge to the global Phase 1 study NI-0501-03 where single dose administration of 0.01, 0.1, 1 and 3 mg/kg were administered.

Because the PK of emapalumab in healthy adults is linear, one dose level is sufficient for a comparison between Japanese and non-Japanese. Also, a single dose is sufficient to compare PK between Japanese and non-Japanese, since the PK of emapalumab does not show any time-dependency upon repeated-dose since administration.

The global Phase 1 study (NI-0501-03) in 20 healthy adult volunteers investigated the safety, tolerability and PK profiles of single IV administrations of emapalumab. During this study 6 subjects received placebo, while 3, 3, 4, and 4 subjects (in total 14 subjects) received emapalumab doses of 0.01, 0.1, 1, and 3 mg/kg, respectively. All IMP infusions were uneventful, and most AEs were singular occurrences and no trend in relation to increasing emapalumab dosage was observed.

The PK analysis of emapalumab in the NI-0501-03 study revealed the expected profile for an IgG1 with a long half-life (around 22 days), a slow clearance (≤ 0.1 mL/kg/hr) and a low volume of distribution (<65 mL/kg on average). The serum concentrations following 1 mg/kg were

pharmacologically relevant since Cmax (32 200 ng/mL) was approximately 50 times the IC50 (603 ng/mL) for significant neutralization of IFN γ .

Considering the scaling factor from the Non-human primate to human (x0.32). 30 mg/kg (NO AEL) which was very well tolerated in monkeys, with no adverse clinical signs or organ toxicity reported, correspond to a HED of 10 mg/kg, therefore the 30 mg/kg in monkey is 10-fold higher than the starting dose in human of 1 mg/kg

Taken these aspects into account, a single intravenous dose of 1 mg/kg emapalumab has been selected for the Phase 2-3 study in pHLH thus this dose is selected also for this study in Japanese healthy subjects.

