6.7 Pharmacokinetic, pharmacodynamic and safety assessments

6.7.1 Study schedule

Table 4 describes the study schedule.

Table 4

Schedule of Events

Assessments		Screening Visit (21 days)	Study Day -1	Treatment – Study Day							Study Days 2-8				Follow-up Wks 2, 4, and 6 (± 2 days for all visits)	Follow-up Wks 8, 10, and 12 (± 2 days for all visits)	Study Completion Visit (w14- ± 2 days) or withdrawal (WD)	Unscheduled Visit				
				1							2	3	5	8								
				Pre-infusion	1h post start	2h post start	4h post start	8h post start	10h post start	12h post start												
Subject Information	Informed Consent	X																				
	Demographic	X	x																			
	Medical history	X																				
	Eligibility criteria	X	x	x																		
	Randomization			x																		
Physical Examination	Vital Signs ¹	X	x		every 30 min	every hour	every 2h	x	x	x	x					x	x					
	12-lead ECG	X		x		x											x					
	Physical Examination ²	X	x													x	x					
	Body weight	X	x														x					
Laboratory procedure	Viral serology and Infections ³	X																				
	Microbiology testing for shigella and salmonella bacteria (stool)	X																				
	s-HCG	X	x																			
	Hematology/Chemistry ⁴	X	x			x			x	x	x	x	x	x ⁵	X	x						
	Urine Pregnancy Test ⁶													x	x	x						
	Urinalysis ⁷	X	x			x			x	x	x	x	x		x	x	x					
	TB testing (Quatiferon/T-spot)	X																				

Assessments		Screening Visit (21 days)	Study Day -1	Treatment – Study Day							Study Days 2-8				Follow-up Wks 2, 4, and 6 (±2 days for all visits)	Follow-up Wks 8, 10, and 12 (±2 days for all visits)	Study Completion Visit (w14-±2 days) or withdrawal (WD)	Unscheduled Visit				
				1							2	3	5	8								
				Pre-infusion	1h post start	2h post start	4h post start	8h post start	10h post start	12h post start												
	PCR – SARS-CoV-19 ⁸	X																				
	Alcohol and drug screen		x																			
PK				x	x ⁹	x	x	x	x	x	x	x	x	x	x	x	x	x				
PD				x	x	x	x	x	x	x	x	x	x	x	x	x	x	x				
Immunogenicity				x														x				
SAE/AE		X	x	x	x	x	x	x	x	x	x	x	x	x	x	x	x	x				
Concomitant Medication				x	x	x	x	x	x	x	x	x	x	x	x	x	x	x				

1. Body weight and height will be collected at Screening, and body weight at Study Day -1 and Week 14
2. A full physical examination will be performed at screening. And at Week 4 visit. At all other visits brief physical examinations will be performed, only if indicated.

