6.7.7.2.7 Follow-up of pregnancy

Any pregnancy must be followed to its conclusion, and its outcome must be reported to the Sobi safety department.

Such follow-up information will only be entered in the sponsor's safety database, and hence will not affect study closure. Table 5 presents the laboratory assessments.

Table 5 **Laboratory Assessments**

Biochemistry	Hematology
Aspartate aminotransferase (AST)	Hemoglobin
Alanine aminotransferase (ALT)	Hematocrit
Direct Bilirubin	Platelet count
Total Bilirubin	White blood cells
Uric acid	Red blood cells
Alkaline phosphatase	Differential blood count
Total Protein	Immunoglobulin levels
Albumin	Coagulation profile (APTT)
Prothrombin Time/International Normalized Ratio (PT-INR)	
Fibrinogen	
Complement C3/C4	
Cardiac troponin	
Creatinine	
C-reactive protein (CRP)	
Electrolytes (Sodium, Potassium, Calcium)	
Glucose	
Lipids (fasting (except screening) triglycerides, HDL, LDL)	
BUN/Urea	
Urinalysis (dipstick)	
	Erythrocytes, Leukocytes
	Glucose
	Ketones
	pH
	Protein
	Sediment (only if positive results are obtained for Protein, Erythrocytes and leukocytes measurements)
	Urine pregnancy test
Additional testing at screening	
	TB screening (Quantiferon/T-spot)
	PCR SARS-CoV-2
	Viral serology and infections (HBV, HCV, HIV and syphilis)
	Microbiology testing (stool) for shigella and salmonella bacteria
	s-HCG
	Drug screen;
	Benzodiazepines, cocaine, methamphetamines, marijuana, barbiturates, morphine, Phencyclidines and tricyclic antidepressants

All laboratory samples will be analyzed at the local laboratory of the phase I unit according to their standard routines.

Clinically significant laboratory values should be reported as AEs (see Section 6.7.7.1.1 for details).

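### Stool screening leaves out Campylobacter, one of the two enteric infections reported in carrier monkeys, and the roughly 10-fold dose margin is not shown for carriers

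*Protocol*

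**What the plan says.** **Screening.** Protocol 6.5.2, exclusion 6, is "Positive stool test for Shigella or salmonella infection". The stool row of Table 4 (6.7.1) is marked at screening only and names the same two organisms. Table 5 repeats them: "Microbiology testing (stool) for shigella and salmonella bacteria". SAP 4.2 refers back to the protocol for eligibility and adds nothing.

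**Toxicology.** Protocol 4.1.2.2.2 states: "Shigella and Campylobacter infections were observed at all dose levels (10 to 200 mg/kg/week) in animals originally harboring gastrointestinal pathogens". The organisms listed as carried beforehand are Shigella, Salmonella and Campylobacter. On cause it says: "These findings were assessed to be in line with emapalumab pharmacological effect", because IFN-gamma helps to control these organisms. In a later study the "cynomolgus monkeys were free from gastrointestinal pathogens at Screening"; weekly doses up to 30 mg/kg for 8 weeks were well tolerated, without gastrointestinal disturbance.

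**Dose rationale.** Protocol 6.6.3 takes 30 mg/kg as the NOAEL, "which was very well tolerated in monkeys, with no adverse clinical signs or organ toxicity reported". It converts this with a factor of 0.32 to a human equivalent dose (HED) of 10 mg/kg and describes a 10-fold distance from the 1 mg/kg study dose. It does not say which monkey study supplied the NOAEL.

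**The concern.** The protocol names two enteric infections that appeared in carrier animals under IFN-gamma neutralisation. It tests volunteers for one of them (Shigella), and for a third organism (Salmonella) that was carried but is not reported as a resulting infection. Campylobacter appears in 4.1.2.2.2 and nowhere else in the protocol.

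Two things are at stake. The first is the safety of healthy volunteers, who gain no benefit and for whom 4.4 promises every effort to limit risk: a symptom-free Campylobacter carrier can pass every listed entry test. The second is the reach of the margin in 6.6.3. If it comes from pathogen-free animals, it describes a population that the entry criteria do not fully reproduce.

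**Working it through.** **1. The passages side by side**

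| Organism | Carried by monkeys before dosing (4.1.2.2.2) | Infection reported on treatment (4.1.2.2.2) | Volunteer stool test (6.5.2, Tables 4 and 5) |
|---|---|---|---|
| Shigella | yes | yes, all dose levels | yes |
| Salmonella | yes | not reported | yes |
| Campylobacter | yes | yes, all dose levels | no |

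**2. Do other criteria close the gap?** Exclusion 4 bars any bacterial infection in the 4 weeks before infusion but names no test. Inclusion 5 requires a normal CRP, which is not a test for carriage. Together they would catch a known or symptomatic infection. Undetected, symptom-free carriage remains. The protocol itself tests stool for two organisms in addition to these criteria.

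**3. The plan's own figure.** HED = monkey dose x 0.32 (6.6.3).
- NOAEL: 30 x 0.32 = 9.6 mg/kg, which rounds to the stated 10 mg/kg. Against 1 mg/kg this is 9.6-fold, so the stated 10-fold is reproduced on the HED scale.

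**4. The same conversion for carriers.**
- Lowest dose reported: 10 x 0.32 = 3.2 mg/kg per dose, 3.2 times the study dose.
- If those animals had the full 13 weekly doses mentioned in the same paragraph: 13 x 3.2 = 41.6 mg/kg HED in total, against one dose of 1 mg/kg here.
- Infections occurred at all levels from 10 mg/kg/week upward, so no infection-free dose is reported in carriers. Nothing below 3.2 mg/kg HED is reported in them either.

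**5. Source of the NOAEL.** The 30 mg/kg in 6.6.3 equals the top dose of the pathogen-free study, and the tolerability description agrees. It cannot describe the carrier animals. That it comes from the pathogen-free study is an inference, since 6.6.3 names no source.

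**6. How likely is a carrier?** The documents give no carriage frequency. As an assumption only, take p from 0.5% to 5% and compute P(at least one carrier) = 1 - (1 - p)^n.

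| Assumed p | n = 6 (emapalumab) | n = 8 (all subjects) |
|---|---|---|
| 0.5% | 3.0% | 3.9% |
| 1% | 5.9% | 7.7% |
| 2% | 11.4% | 14.9% |
| 5% | 26.5% | 33.7% |

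These are chances of enrolling a carrier, not of an infection.

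**The case against.** **There is no contradiction.** Exclusion 6, Table 4 and Table 5 agree with one another, and nothing obliges the screen to cover every organism found in the animals. This stands: what is missing is a target or a reason for leaving it out.

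**The animal exposure was far higher and repeated.** This also stands. In addition, 4.1.2.2.2 gives no infection counts, no control rate and no time of onset. A reader might infer that the protocol's own data predict infection in a dosed carrier. They do not: 1 mg/kg lies below anything reported in carriers, so the data leave the question open. The single dose does not settle it the other way, because exposure is long. With the figures in 6.6.3, 1 mg/kg over a volume below 65 mL/kg gives at least about 15.4 µg/mL. That is about 25 times the IC50 of 603 ng/mL, or log2(25.5) = 4.7 half-lives. At about 22 days each, this is roughly 100 days. It is a crude mono-exponential estimate of time above the IC50, not evidence of infection.

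**Human experience shows no Campylobacter case.** Protocol 4.1.2.3 and 4.4 mention histoplasmosis, Salmonella gastroenteritis and herpes zoster. The list of specific pathogens in 4.4 omits Campylobacter, but it also omits Shigella, which is screened, so it does not explain the choice.

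**The margin is not the only support for the dose.** True: 6.6.3 also cites 14 healthy volunteers given up to 3 mg/kg, and 4.4 cites doses up to 10 mg/kg in other studies. The point about the margin concerns only how far that statement reaches.

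**Conclusion.** The concern holds in a limited form. Stool screening omits one of the two organisms that the protocol reports as causing infection in carrier animals, without a stated reason, and no other entry criterion detects symptom-free carriage of it. The roughly 10-fold margin (9.6-fold on the protocol's factor) is not shown for carriers.

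The size of the risk cannot be stated. Carriage frequency is not given, and the carrier data start at 3.2 mg/kg HED per dose, given repeatedly. The link between the NOAEL and the pathogen-free study rests on the equal dose and similar description, not on a citation.

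Two further consequences might be inferred but are not supported:
- **Stopping rules.** Protocol 6.3 requires a qualifying severe infusion reaction, severe findings in two or more subjects, a life-threatening or fatal event, or the investigator's judgement of unacceptable risk. One non-life-threatening enteric infection meets no automatic rule.
- **Biomarkers.** No figure in the documents shows that such an infection would disturb the IFN-gamma, CXCL9 or sIL2R readings.

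Sample size and the planned analyses are unaffected. The change is still worth making because it is cheap and addresses a hazard that the protocol's own toxicology section describes.

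**What to change.** - Reconcile exclusion 6 (6.5.2), the stool row of Table 4 and the stool line of Table 5 with 4.1.2.2.2. Either include Campylobacter as a target on the stool sample already collected at screening, or state why it is not needed.
- In 6.6.3, name the study behind the 30 mg/kg NOAEL and say that the margin is not shown for carriers of enteric pathogens.

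The cost is one more laboratory target per screened volunteer and possibly an occasional extra screen failure. No new visit is needed. The documents do not describe the stool method, so the local laboratory should confirm that the same sample will serve.
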